to continue to track their AF frequency and severity for 4 more weeks. During this 4 week period, participants will be able to implement any lifestyle changes they deem appropriate based on what they learned from their N of 1 trial. Following the completion of the 4 week "lifestyle change" period, participants will complete the AFEQT survey and will then have the option of either testing another AF trigger or concluding their study participation. Participants that choose to test additional triggers will have up to one week to start their next N-of-1 trial that will follow the same trigger testing protocol as the first. Participants will have the option of testing up to 5 triggers following this protocol.

Symptom Surveillance: Participants randomized to the symptom surveillance arm will engage in data tracking for a period of 10 weeks and receive daily reminders to complete study activities. Participants will be asked daily about the estimated total duration and severity of AF episode(s) and daily mood and sleep quality. They will also be asked to take AliveCor readings at least once per day and anytime they are experiencing AF symptoms. Participants will be able to visualize their AF data in real time and will receive a monthly summary of their AF frequency and severity via the Eureka app. At the end of the 10-week tracking period, participants will complete the AFEQT survey. Then, participants will have the option to cross over to engage in trigger testing. Participants that choose to test their triggers will be able to test up to 4 triggers, one trigger at a time, following the N-of-1 trial protocol described above.

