1.8 Safety and Adverse Events (AE)

1.8.1 Adverse Event Reporting

Participants will receive monthly prompts via the application about the following things: hospitalizations (AF, emergency department, cerebrovascular event, myocardial infarction or heart failure), antiarrhythmic medication changes and ablation plans.

We will share reports with the DSMB outlining the results of the above survey.

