4.1 Measures

Data that will be collected during the study are detailed in Table 2:

Construct	Measure(s)	Categorization	Timing	Source	
Primary Outcome (comparing N-of-1 group to data tracking group)					
Atrial fibrillation quality of life	AFEQT score	Integer (20-140). Survey includes 20 questions 1-7	Baseline and 10 weeks	Eureka app	
		score for each			
Primary Outcomes	(for individual-level	N-of-1 trials within th	e N-of-1 group)	Γ	
Atrial fibrillation	ECG flagged by	1=Yes	Daily and whenever	AliveCor app	
device	algorithm	U=INO	a symptomatic		
Atrial fibrillation	Patient report	1=Yes 0=No	Daily	Eureka app	
Atrial fibrillation duration	Patient report (hrs and minutes)	Integer 0-60 hrs, 0-60 min	Daily (queried only if self-reported atrial fibrillation=Yes on that day)	Eureka app	
Atrial fibrillation severity	Patient report	Integer 1-7, ordinal scale 1=least severe	Daily (queried only if self-reported atrial fibrillation=Yes on that day)	Eureka app	
SECONDARY ENDPOINTS					
AliveCor confirmed atrial fibrillation event	Patient reported atrial fibrillation event confirmed	1=Yes 0=No	Daily and whenever a symptomatic episode occurs	AliveCor app and Eureka app	

Table 2

within the N-of-1 group and compared to data tracking in last	by report from AliveCor device			
Count of AF Frequency	The number of patients reported AF episodes during the final month of enrollment	Integer 0-7—count	Daily	Eureka app
Total duration of AF episodes	Total duration of patient reported AF episodes daily during the final month of enrollment	Continuous 0-60 min, 0-24 hours 0= no answer	Daily (only if self-reported atrial fibrillation=Yes on that day)	Eureka app
Average severity of AF episodes	average severity of patient reported AF episodes daily during final month of enrollment	Continuous (range 1-7 using, Ordinal Scale 1=least severe 0= no answer	Daily (only if self-reported atrial fibrillation=Yes on that day)	Eureka app
Safety Measures Emergency room visit	Patient report	1=Yes 2=No 3=Don't know If yes, date and hospital location	Monthly: Reported at 4 & 8 weeks; actual emergency room visits will be categorized by day	Eureka app
Emergency room visit related to atrial fibrillation	Patient report	1=Yes 2=No 3=Don't know	Monthly (queried only if emergency room visit=Yes for that month) Reported at 4 &8 weeks.	Eureka app

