Hospitalization	Patient report	1=Yes 2=No 3=Don't know If yes, date and hospital location	Monthly; actual hospitalizations will be categorized by day reported at 4 and 8 weeks.	Eureka app
Hospitalization related to atrial fibrillation	Patient report	1=Yes 2=No 3=Don't know	Monthly (queried only if hospitalization=Yes for that month)	Eureka app

			Reported at 4 &8	
			weeks.	
Cerebrovascular accident	Patient report	1=Yes 2=No 3=Don't know If yes, date and location diagnosis	Monthly; reported at 4 &8 weeks.	Eureka app
Myocardial infarction	Patient report	made 1=Yes 2=No 3=Don't know If yes, date and location diagnosis made	Monthly; reported at 4 &8 weeks.	Eureka app
Heart failure	Patient report	1=Yes 2=No 3=Don't know If yes, date and location diagnosis made	Monthly; reported at 4 &8 weeks.	Eureka app
MODIFIERS	_			
Age	Patient report	Continuous	Baseline only	Eureka app
Gender Identity	Patient report	1=Woman 2=Man 3=Transgender Woman 4=Transgender Man 5=Genderqueer 6=Another gender identity 7=Decline to state	Baseline only	Eureka app
Sex	Patient report	1=Male 2=Female 3=Prefer not to state	Baseline only	Eureka app
Race	Patient report	1=Black 2=White 3=Asian 4=Native Hawaiian or Pacific Islander 5=American Indian or Alaska Native 6=Some other race 7=Don't know	Baseline only	Eureka app

		8=Prefer not to		
		state		
Hispanic	Patient report	1=Not Hispanic 2=Yes: Mexican, Mexican American or Chicano 3=Yes: Puerto Rican 4=Yes: Cuban 5=Yes: Cuban 5=Yes: Mixed Hispanic, Latino or Spanish Origin 6=Yes: Other Hispanic, Latino, or Spanish Origin 7=Don't know 8=Prefer not to state	Baseline Only	Eureka app
Education level	Patient report	1=No formal schooling 2=Some school, but did not graduate high school 3=High school diploma or equivalent 4=Associate degree 5=Some college 6=Bachelor's degree 7=Master's degree 8=Doctorate 9=Professional doctorate 10=Other 11=Don't know 12=Prefer not to state	Baseline Only	Eureka app
Household income	Patient report	1= Under \$10,000 2= \$10,000 to under \$20,000 3= \$20,000 to under \$30,000	Baseline Only	Eureka App

		4=\$30,000 to		
		under \$40,000		
		5= \$40,000 to		
		under \$50,000		
		6= \$50,000 to		
		under \$75,000		
		7= \$75,000 to		
		under \$100,000		
		8= \$100,000 to		
		under \$150,000		
		9= More than		
		\$150,000		
		10= Don't know		
		11= Prefer not to		
		state		
Household size	Patient report	Integer 0-20	Baseline Only	Eureka app
Hoight	Dationt report	Integer 1 10 ft	Pacolino Only	Euroka ann

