4.4. Safety Endpoints

- 1. **Hospitalization** Days on which any hospitalization occurs together with date and hospital location. This will be recorded from the Eureka app and will be reported monthly by the patient.
- 2. **Hospitalization related to atrial fibrillation** Days on which a hospitalization related to atrial fibrillation occurs together with date and hospital location. This will be recorded from the Eureka app and will be reported monthly by the patient.
- 3. **Emergency department visit** Days on which any emergency department visit occurs together with date and hospital location. This will be recorded from the Eureka app and will be reported monthly by the patient.
- 4. **Cerebrovascular accident** Days on which any cerebrovascular accident occurs together with date and hospital location. This will be recorded from the Eureka app and will be reported monthly by the patient.
- 5. **Myocardial infarction** Days on which a myocardial infarction occurs together with date and hospital location. This will be recorded from the Eureka app and will be reported monthly by the patient.
- 6. **Heart failure** Days on which heart failure occurs together with date and hospital location. This will be recorded from the Eureka app and will be reported monthly by the patient using language from previous HeH surveys.

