5.4 Analysis

5.4.1 Comparison of N-of-1 to data tracking

The experimental design for Aim 2 is a two-arm randomized trial comparing N-of-1 vs. symptom surveillance. The primary endpoint is AF severity via the AFEQT from baseline to 10 weeks. Differences between treatment groups will be compared using analysis of covariance with the 10 week measurement as the outcome and the baseline measurement as covariate. We will also test for an interaction between treatment and baseline AFEQT in order to measure possible treatment effect heterogeneity. The average frequency, duration and severity of AF episodes per week during the final month of each patient's enrollment will be secondary outcomes. Their group means will be compared with a t-test. Additional secondary outcomes will include safety events: hospitalizations, emergency room visits, stroke, myocardial infarctions and heart failure. The main analysis will treat each of these as a binary outcome indicating the incidence of any event. We will also investigate models for multiple Version 1.0 5/12/17

events per person if these are common. We will check for balance in covariates across the randomized groups and will adjust for any imbalances by including those covariates in regression analyses and reporting the adjusted treatment effect as a secondary analysis. The null hypothesis of no difference will be tested at a significance level of 0.05.

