5.4.3 Meta-Analysis of N-of-1 Trials

We will conduct separate meta-analyses of each set of N-of-1 trials that test a particular trigger. We expect this will likely be most relevant to the triggers offered in the menu which patients are more likely to try and which were also the most commonly identified triggers in a survey recently sent to 1,000 AF patients. The meta-analyses will use the same Bayesian multilevel methods as those outlined in Aim 1 and will be applied to the outcomes of AF events, duration and severity as well as the safety endpoints listed in Table 2. We will use distribution and link functions appropriate to the scale of each outcome variable. We will calculate the average treatment effect in the group of patients as well as the individual effects adjusted for the other patients.

Patients with AF are particularly interested in whether certain triggers are more likely than others to induce AF. Because patients in this study will be choosing to study different triggers and often will be conducting more than N-of-1 trial, the set of trigger comparisons will form a network of triggers (plus no trigger) that may be analytically compared using methods of network meta-analysis.²⁵ Triggers may then be compared indirectly through the common control using techniques from network meta-analysis. The complicating factor here is that trials done by the same patient will be correlated and it will be necessary to adjust for this correlation in the network meta-analysis model. This can be done in two different ways. The first would be to treat each patient's trials as separate and introduce a common patient effect into a Version 1.0 5/12/17

mixed model. The second would be to combine all the trials for a patient into one trial with several arms, one for each different trigger and one for no trigger that would combine all the results from the no trigger arms. If a patient changed the control (no trigger) arm in a new trial (e.g., by testing two triggers vs. one trigger), then the control arm would be analyzed according to the trigger used. This approach would create multi-arm trials for patients with multiple trials. These would then be analyzed by methods for multi-arm studies in a network meta-analysis.

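### SAP Table 2 lists safety reports at weeks 4 and 8 only, other sections set no end, and the any-event arm comparison has no time window: the safety schedule and window need to be reconciled

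*SAP*

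**What the plan says.** **Schedule.** In SAP 4.1, Table 2, the emergency room row is timed "Monthly: Reported at 4 & 8 weeks". The stroke, myocardial infarction and heart failure rows read "Monthly; reported at 4 &8 weeks", and the hospitalisation rows are equivalent. No later time point is listed. SAP 4.4 says that each safety endpoint "will be reported monthly by the patient", and Protocol 1.8.1 says "Participants will receive monthly prompts via the application". Neither gives an end.

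**Time on study.** Protocol 1.4.1 and 1.5 set a 6-week N-of-1 trial (three exposure weeks, three elimination weeks) followed by a 4-week lifestyle period. For the N-of-1 arm, "Participants will have the option of testing up to 5 triggers following this protocol". Surveillance participants track for 10 weeks; those who then cross over "will be able to test up to 4 triggers, one trigger at a time". SAP 5.4.3 expects that patients will often run more than one trial.

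**Analysis.** SAP 5.4.1 compares the arms on hospitalisation, emergency visits, stroke, infarction and heart failure: "The main analysis will treat each of these as a binary outcome indicating the incidence of any event". It states no time window, no rule for crossover and no person-time denominator. SAP 5.4.1.2 takes days without a reported safety event to be event-free, so that nothing is missing. SAP 5.4.3 applies the trigger-level meta-analyses to AF outcomes "as well as the safety endpoints listed in Table 2".

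**The concern.** The plan does not settle how long safety is collected or over what time the arms are compared. Each plausible answer damages a different analysis.

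If collection follows Table 2, time in which nobody was asked is analysed as time in which nothing happened. That biases the trigger-level safety analyses towards no harm for participants who test several triggers or cross over.

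If collection follows the open-ended wording, the between-arm comparison mixes randomised time with time after optional continuation and crossover. A surveillance participant's stroke or admission during later trigger testing is then counted against surveillance, which can hide a harm. If more people continue in one arm than in the other, that arm has longer to accrue events, which can create an apparent harm.

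**Working it through.** The plan gives no safety event rate and no length of safety follow-up, so it has no figure of its own to reproduce here. Its 239 per group is sized on AFEQT and has no bearing on the schedule question.

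**Step 1: length of enrolment.** One cycle is 6 + 4 = 10 weeks (Protocol 1.4.1). Protocol 1.5 allows up to 1 week between trials.
- N-of-1 arm, k triggers: 10k to 10k + (k − 1) weeks. For k = 5 this is 50 to 54 weeks.
- Surveillance arm, m triggers after crossover: 10 + 10m to 10 + 11m weeks, assuming the same gap of up to 1 week before each trial. For m = 4 this is also 50 to 54 weeks.

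The maximum is therefore the same in both arms.

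**Step 2: Table 2 read literally, with queries at weeks 4 and 8 of enrolment only.** Crossover starts after week 10, so what is collected covers equal, uncrossed time. Three gaps remain:
- Weeks 8-10 of the randomised period, 2 of 10 weeks (20%) in both arms, follow the last query.
- First-trial exposure falls in weeks 1-6 and is covered by the week-8 query. Exposure after the last query is 3(k − 1) of 3k weeks:

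| Triggers tested (N-of-1 arm) | Exposure weeks | After last query |
|---|---|---|
| 1 | 3 | 0 (0%) |
| 2 | 6 | 3 (50%) |
| 3 | 9 | 6 (67%) |
| 4 | 12 | 9 (75%) |
| 5 | 15 | 12 (80%) |

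- For a crossover participant, every exposure week follows the last query, up to 4 × 3 = 12.

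At the maximum, 50 − 8 = 42 weeks (84% of 50) to 54 − 8 = 46 weeks (85% of 54) of enrolment have no listed query. SAP 5.4.1.2 is the only missing-data rule that names safety events, and it makes this time event-free. It sits under the arm comparison. SAP 5.4.3.3 gives the same rule for unreported AF days and is silent on safety, so I take 5.4.1.2 to carry over to the trigger-level analyses.

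**Step 3: open-ended monthly prompts.** All enrolment is queried, but the any-event outcome has no window. A surveillance participant who tests four triggers spends 40 of 50 weeks (80%) in N-of-1 cycles and stays in the surveillance count.

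*Illustrations only.* Constant weekly hazards h of 0.1% to 1% are my assumption, with risk over t weeks = 1 − exp(−ht).

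(a) Crossover. Suppose N-of-1 time truly doubles the hazard and everyone stays 54 weeks, with surveillance crossing over at week 10. The N-of-1 risk is 1 − exp(−2h·54) and the surveillance risk is 1 − exp(−10h − 2h·44).

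| h per week | First 10 weeks | Ratio | All 54 weeks | Ratio |
|---|---|---|---|---|
| 0.1% | 2.0% v 1.0% | 1.99 | 10.2% v 9.3% | 1.10 |
| 0.5% | 9.5% v 4.9% | 1.95 | 41.7% v 38.7% | 1.08 |
| 1% | 18.1% v 9.5% | 1.90 | 66.0% v 62.5% | 1.06 |

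(b) Differential continuation. Suppose there is no true effect, one arm is followed for 10 weeks and the other for 21 (two cycles and a gap). With 239 per arm and a two-sided 0.05 test of two proportions:

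| h per week | 10 weeks | 21 weeks | Chance of nominal significance |
|---|---|---|---|
| 0.1% | 1.0% | 2.1% | 16% |
| 0.5% | 4.9% | 10.0% | 57% |
| 1% | 9.5% | 18.9% | 84% |

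Both scenarios are deliberately extreme in who continues. They show direction and possible scale and do not forecast this trial.

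**The case against.** **Table 2 may not mean that collection stops.** The timing cell begins with the word monthly, SAP 4.4 and Protocol 1.8.1 agree, and weeks 4 and 8 are the monthly points inside a 10-week cycle. Table 2 also lists AFEQT at baseline and 10 weeks, although SAP 2 has it completed after each lifestyle period, so the table may describe only the first cycle. A reader might infer that safety collection definitely ends at week 8 and that most prompted exposure goes unmonitored. The documents do not support that: no passage says queries end, and the missed share is 0% for a participant with a single trial. What stands is that the per-cycle reading is nowhere stated. It also leads back to an arm comparison without a window. And it leaves weeks 8-10 of a participant's last cycle unqueried, while those who continue could report those weeks at their next survey.

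**A reader might infer that both harms occur together.** They cannot, because each belongs to a different reading. With Table 2 taken literally, the arm comparison is not confounded by crossover or follow-up time.

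**A reader might infer that longer follow-up in the N-of-1 arm is built in.** It is not. Both arms can reach about 50-54 weeks, the imbalance depends on who continues, and the documents give no continuation rate. The direction could go either way. Crossover contamination does not need unequal time, but it arises only on the open-ended reading.

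**A 10-week window may be implied.** The SAP executive summary speaks of a 10-week study period, but ties it to the AFEQT survey. SAP 5.4.1 defines its other secondary outcomes by the last month of each patient's enrolment, so a 10-week limit on safety cannot be presumed.

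**The trial is described as low risk and these are secondary outcomes.** This is true and limits the importance of the point. The SAP nonetheless plans to compare the arms on these events, and DSMB reports draw on them.

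**Conclusion.** The concern holds as an unreconciled schedule combined with an undefined comparison window.

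- If Table 2 governs, the arm comparison is fair as far as it goes. Weeks 8-10, later trials and crossover trials have no listed query, and that time would be counted as event-free. This is up to 12 of 15 exposure weeks for five triggers, none for one trigger, and all exposure weeks (up to 12) for crossovers.
- If open-ended prompts govern, collection is adequate, but the any-event comparison counts events during crossover trigger testing against surveillance and is exposed to any difference in continuation.

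The week counts follow from the protocol, with the one gap assumption noted in the working. The risk ratios and false-positive chances rest on event rates and continuation patterns that I assumed. The trigger-level consequence also assumes that the event-free rule in SAP 5.4.1.2 carries over to SAP 5.4.3. The primary AFEQT analysis and the sample size are not affected. The change should be made, because the planned safety analyses cannot be interpreted until one reading is fixed.

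**What to change.** 1. **SAP Table 2, SAP 4.4 and Protocol 1.8.1:** state one schedule. Send the existing safety survey at weeks 4, 8 and 10 of the initial period in both arms, and at the same points of every later or crossover 10-week cycle. The week-10 survey can accompany the AFEQT already due then.
2. **SAP 5.4.1:** limit the between-arm any-event comparison to events dated from display of the assigned arm to the end of the initial 10 weeks, before any crossover. Event dates are already collected.
3. **SAP 5.4.1.2 and 5.4.3:** do not count time that no completed safety survey covers as event-free. Use events from later and crossover trials only in the trigger-level analyses.

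**Cost:** app scheduling of a survey that already exists, SAP and protocol wording, and a few more short surveys, mainly for participants who choose further trials. The between-arm comparison will contain fewer events than one over all enrolment, which is the price of comparing equal, uncrossed time.

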4.2. Primary Endpoints

- 1. **Atrial fibrillation quality of life** will be measured by the AFEQT survey monthly and will be used in comparing of the N-of-1 arm to the tracking arm. The primary outcome will be change from baseline (randomization) to 10 weeks.
- 2. **Self-reported atrial fibrillation event** Each day patients will report if they have had an atrial fibrillation event.
- 3. Atrial fibrillation duration Each day patients will report the total amount of time during which they had atrial fibrillation adding up time over all events over the day. For days on which no event occurred, the time will be zero.

4. **Atrial fibrillation severity** Each day patients will record the severity of their atrial fibrillation on a scale of 1-7 with a score of 1 given if no event occurred.

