1.5 Study Procedures

Randomization/Baseline evaluation: Potential participants will be identified via the Health eHeart Study and the StopAfib.org patient advocacy organization and reached out to via email campaigns. Of note, invitations will be extended broadly to include friends family and acquaintances of those participants. Patients may also be recruited directly from UCSF clinics or other web-based sources of potentially interested atrial fibrillation patients. The study email campaign will contain an overview of the study. If the patient is interested in participating in the study there will be a link for the participant that will take them to the mobile app store to

download the Eureka app. Potential participants will be prompted to register an account and will complete an inclusion/ exclusion criteria survey within the Eureka app. If eligible, they will continue on to the study consent form (Appendix B). Upon completion of the electronic study consent, Eureka will randomize participants to either the N-of-1 or the symptom surveillance arm of the study with a 1:1 allocation ratio.

Participants will then be asked to complete baseline data collection which will include basic demographics, medical history, and current atrial fibrillation medications. After baseline data collection, the study team will ship AliveCor devices to study participants over a period of two weeks. At the end of this two week period, participant will be prompted to visit the Eureka application to complete a device consent and then will be instructed to download the AliveCor app and link their AliveCor device to their Eureka account. All participants will then complete the Atrial Fibrillation Effect on QualiTy of Life survey (AFEQT) (Appendix A). Once they complete the survey, the app will show participants which study arm they have been randomized to and prompt them to begin the appropriate study activities.

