N-of-1 Trial arm: Patients will use the Eureka mobile application and AliveCor device to execute at least one N-of-1 trial with the goal of identifying and better controlling their AF triggers. Each N-of-1 trial will last a total of 6 weeks and will include up to 3 periods of trigger exposure and 3 periods of trigger elimination with each exposure/elimination period lasting 1 week. Patients will be randomly assigned a sequence of trigger exposure and elimination periods such that they receive each treatment in each two-week block. During each N-of-1 trial, patients will track daily AF duration and severity, daily mood and sleep quality, daily AliveCor tracings and daily trigger exposure. At the end of each trial, patients will be able to review their trial results which will include visualizations of their daily AF symptom and trigger tracking over time. After completing a trial, patients will be instructed to implement any lifestyle changes they deem appropriate based on what they learned from the results of their trial. Patients will implement these changes for a period of 4 weeks during which they will continue to track AF episode duration and severity via the app. At the end of the 4-week lifestyle change period, patients will complete the Atrial Fibrillation Effect on Quality of Life survey (AFEQT) (Appendix A) and will then have the option of testing another trigger or ending their study participation.

Symptom Surveillance arm: Patients will use the Eureka app and AliveCor device to record daily AF duration and severity, daily AliveCor readings and daily mood and sleep quality for a period of 10 weeks. Patients will be able to visualize their AF, sleep and mood data in real time and will receive a weekly summary of their data via the Eureka app. At the end of the 10-week data tracking period, patients will complete the AFEQT survey and will then have the option of either ending their study participation or crossing over to the N-of-1 trial arm to test their triggers.

Primary Study Aim:

To test the comparative effectiveness of N-of-1 trials vs. data tracking alone to identify and eliminate individual level triggers and reduce AF frequency and severity as measured by the atrial fibrillation quality of life scale (AFEQT)

Secondary Aims:

- Using individual N-of-1 trials, identify modifiable exposures that increase the risk for an AF episode on an individual-level.

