5.3 Randomization to Treatments

Completion of the electronic consent via the Eureka portal will trigger 1:1 randomization to the N-of-1 or the symptom surveillance conditions. The randomization schema will be conducted within the Eureka platform and communicated directly to patients via the mobile app.

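### The primary endpoint has no single time origin: SAP 4.2 counts 10 weeks from randomisation, but the baseline AFEQT and arm activities start at least two weeks later, and Protocol 1.7.2 says 12 weeks

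*SAP*

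**What the plan says.** The documents give several accounts of when the primary endpoint starts and ends.

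- **SAP 4.2 (Primary Endpoints):** "The primary outcome will be change from baseline (randomization) to 10 weeks". The same paragraph says the AFEQT is measured monthly, whereas SAP Table 2 lists it only at baseline and 10 weeks.
- **When randomisation occurs:** SAP 5.3 says "Completion of the electronic consent via the Eureka portal will trigger 1:1 randomization", and Protocol 1.5 agrees: "Upon completion of the electronic study consent, Eureka will randomize participants to either the N-of-1 or the symptom surveillance arm".
- **What follows randomisation (Protocol 1.5):** After baseline data collection, "the study team will ship AliveCor devices to study participants over a period of two weeks". At the end of that period participants are prompted to give device consent and link the device. They then complete the first AFEQT that the protocol describes. "Once they complete the survey, the app will show participants which study arm they have been randomized to", and arm activities begin.
- **When the final AFEQT is due (SAP section 2; likewise Protocol 1.4.1 and 1.5):** For the N-of-1 arm, "At the end of the 4-week lifestyle change period, patients will complete the Atrial Fibrillation Effect on Quality of Life survey". For surveillance, "At the end of the 10-week data tracking period, patients will complete the AFEQT survey".
- **Protocol 1.7.2 (Analysis of Comparative Effectiveness):** The primary outcome runs from baseline to 12 weeks. SAP 5.4.1 says 10 weeks.

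Neither document gives a window around the assessment.

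**The concern.** The AFEQT in Protocol Appendix A asks about the past 4 weeks in 18 of its 20 items; the two satisfaction items ask about the present. The N-of-1 schedule is 6 weeks of trigger testing followed by 4 weeks of lifestyle change. The comparison works as designed only if the 4 recalled weeks are the 4 lifestyle weeks. An origin two weeks too early moves the recall window back into trigger testing in the N-of-1 arm. In the surveillance arm the same shift changes nothing, because every week is tracking.

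Tying the survey to completion of activities raises a different problem. The control survey follows 10 weeks of tracking. The N-of-1 survey follows a trial that begins once the participant has selected a trigger (Protocol 1.5). No limit is stated for starting the first trial, although later ones must start within one week. Participants may opt out of testing a trigger (Protocol 1.6.4), and for those who do so or stall while still enrolled, no end-of-lifestyle moment is defined. Survey timing and missingness could then differ by arm. That matters because Protocol 1.7.2 scores a missing endpoint as no change.

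**Working it through.** **Inputs.** Testing lasts 6 weeks and lifestyle change 4 weeks (SAP section 2; Protocol 1.4.1). AFEQT recall is 4 weeks (Protocol Appendix A). The primary time point T is 10 weeks (SAP 4.2, 5.4.1) or 12 weeks (Protocol 1.7.2). Let L be the lag in weeks from the chosen origin to the start of arm activities. Counted from the baseline AFEQT, L = 0. Counted from randomisation, L is about 2 from shipping alone (Protocol 1.5), plus a linking time that the documents do not give.

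**Reproducing the plan's figure.** 6 + 4 = 10 weeks. This holds when the clock starts at the baseline AFEQT. Counted from randomisation with L = 2, the lifestyle period ends at 2 + 6 + 4 = week 12.

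**Recall composition.** Testing occupies weeks L to L + 6 and lifestyle weeks L + 6 to L + 10. The recall window is weeks T − 4 to T.

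For T = 10 the window is weeks 6 to 10:

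| Lag L | Testing weeks in recall | Lifestyle weeks in recall |
|---|---|---|
| 0 (baseline AFEQT) | 0 | 4 |
| 1 | 1 | 3 |
| 2 (shipping period) | 2 | 2 |
| 3 (assumed) | 3 | 1 |
| 4 or more (assumed) | 4 | 0 |

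At L = 2, testing runs from week 2 to 8 and lifestyle from week 8 to 12. The survey falls at the end of arm week 10 − 2 = 8, and the recall covers arm weeks 5 to 8. Weeks 5 and 6 are testing: one exposure and one elimination week, under the SAP's two-week blocks. Weeks 7 and 8 are lifestyle. The displaced share is 2/4 = 50%.

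For T = 12 (Protocol 1.7.2) the window is weeks 8 to 12:

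- From randomisation with L = 2: 0 testing and 4 lifestyle weeks. This matches the intended window, since 2 + 10 = 12, but the documents do not give that as the reason for 12.
- From the baseline AFEQT (L = 0): 2 lifestyle weeks and 2 weeks after the schedule has ended, when crossover or a second trigger is already open.

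The intended window therefore arises from 10 weeks after the baseline AFEQT, or from 12 weeks after randomisation if the lag is exactly two weeks. SAP 4.2 combines the 10 weeks of the first with the origin of the second.

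**The case against.** The strongest reply is that the problem rests on one parenthesis. No AFEQT is described at electronic consent, so equating baseline with randomisation is most naturally a loose label for the first survey. The passages that schedule the final survey (SAP section 2; Protocol 1.4.1 and 1.5) attach it to the activity schedule, and the SAP Executive Summary places the two surveys before and after the 10-week study period. If the app follows those passages, an on-time N-of-1 participant recalls lifestyle weeks only. The shipping step is also in the protocol, not the SAP. All of this stands and makes the harm conditional. It does not settle which text governs, and it leaves the 12 weeks in Protocol 1.7.2 unexplained.

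Second, the completion-based worry is softened by SAP 5.4.1.2, which plans to seek a 10-week AFEQT from dropouts and lists three missing-data approaches, and by the monthly AFEQT in SAP 4.2. Both points stand in part. The 10-week value has no stated origin, participants who stall or opt out while still enrolled are not mentioned, and the monthly schedule conflicts with SAP Table 2. A reader might infer that such participants are never prompted; no passage says so.

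Third, a calendar survey also puts testing weeks into the recall of anyone who starts late or pauses. That is true, but it affects those participants rather than the whole arm, and it fits a comparison as randomised.

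**Conclusion.** The time origin of the primary endpoint is contradictory across SAP 4.2, SAP section 2, Protocol 1.5 and Protocol 1.7.2, and should be reconciled. Taken literally with a two-week lag, SAP 4.2 would make 2 of the 4 recalled weeks in the N-of-1 arm trigger-testing weeks, for 18 of 20 items, and would allow only 2 of the 4 lifestyle weeks to elapse before the survey. Dilution of a lifestyle-period effect is plausible. The documents give no basis for expressing it in AFEQT points.

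Two stronger readings are not supported. A reader might infer that trigger testing replaces the lifestyle period in the recall altogether. That needs a lag of at least 4 weeks, and any lag beyond the shipping period is an assumption. A reader might also infer a definite bias against N-of-1. The two testing weeks would be one exposure and one elimination week, the sample exposure message in Protocol 1.5 is permissive, and SAP 3.4 says participants face no exposures outside their normal lives. Those weeks need not be worse than control weeks.

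The 50% figure assumes that SAP 4.2 is applied as written, that the lag is two weeks, and that the first trial starts as soon as the arm is shown.

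**What to change.** 1. In SAP 4.2, replace the parenthesis that equates baseline with randomisation by: *the baseline AFEQT completed immediately before the arm is shown (day 0)*.
2. State one primary time point, 10 weeks (day 70) from day 0, with an assessment window, in Protocol 1.7.2, SAP Table 2, SAP 4.2 and SAP 5.4.1. Reconcile the monthly AFEQT in SAP 4.2 with the two time points in Table 2.
3. Send the final AFEQT to both arms at that time, whatever the participant's N-of-1 progress, and before crossover or a second trigger is offered. Align Protocol 1.4.1 and 1.5 and SAP section 2 with this.
4. Record the arm week at survey completion and report it by arm.

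The cost is wording in both documents and one app scheduling rule. The downside is small: participants who start late or pause are surveyed before finishing the lifestyle period. By the table above, a one-week delay puts 1 testing week into the recall. Reporting arm week by arm would show how often this happens.
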